Neuromyelitis optica spectrum disorders (NMOSD)

Ischemic cerebrovascular disorders (e.g., stroke, transient ischemic attack) or ischemia of the spinal cord

Severe, clinically significant brain or spinal cord trauma (e.g., cerebral contusion, spinal cord compression)

Psychosis not yet controlled by a treatment

Drug Related

Systemic, high dose corticosteroid therapy within 4 weeks prior to screening

Contraindications for, or intolerance to, oral or IV corticosteroids, including IV methylprednisolone, according to the country label, including hypersensitivity to any of the treatment drug constituents

Prior exposure to immunomodulatory medications and/or DMT

Prior treatment with any disease modifying therapy for MS including but not limited to: interferon (IFN- β -1a (Avonex, Rebif), IFN- β -1b (Betaseron/Betaferon), glatiramer acetate, dimethyl fumarate (DMF; Tecfidera), diroximel fumarate (Vumerity[®]) fingolimod (Gilenya) or siponimod (Mayzent), ozanimod (Zeposia[®]) natalizumab (Tysabri), alemtuzumab (Lemtrada), cladribine (Mavenclad), rituximab (Rituxan), and other anti-CD20 agents

Previous treatment with cyclophosphamide, mitoxantrone, azathioprine, mycophenolate mofetil, cyclosporine, methotrexate, total body irradiation, or bone marrow transplantation

Previous or concurrent treatment with any investigational agent or treatment with any experimental procedure for MS (e.g., treatment for chronic cerebrospinal venous insufficiency)

Vaccinations: Receipt of a live or live-attenuated vaccine or an inactivated/non-live vaccine within 6 weeks prior to enrollment

Laboratory: Certain laboratory abnormalities or findings at screening, including the following:

Positive serum β -hCG

Positive for hepatitis B (hepatitis B surface antigen [HBsAg] positive or hepatitis B core antibody [total HBcAb] confirmed by positive viral DNA polymerase chain reaction [PCR])

AST or ALT $\geq 3.0 \times$ upper limit of normal

Total white blood cell count, including differential counts, below lower limit of normal

Absolute lymphocyte count below lower level of normal

Absolute neutrophil count below lower limit of normal

Platelet count below lower limit of normal

METHOD OF TREATMENT ASSIGNMENT AND BLINDING

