Randomization and blinding will be employed to minimize bias in treatment assignment and to provide the basis for valid statistical inference. IxRS will be used to assign study identification numbers at the time of signing an informed consent document; this includes close family members undergoing pre-screening as well as those with known RIS who are being screened for the randomized controlled trial. Eligible patients must be randomized through IxRS prior to receiving any study drug. Patients who discontinue treatment for any reason will not be replaced. Under no circumstances are patients who enroll in this study and who have completed treatment as specified, permitted to be re-randomized to this study.

The randomization list will not be available to the study centers, monitors, or to the Sponsor project team. All individuals directly involved in the study will remain blinded to the treatment assignment.

The treatment code will be released to the study team to facilitate analysis of the biological samples collected during this study after the unblinding for the primary analysis has been completed.

Study site personnel and patients will be blinded to treatment assignment until after the primary analysis. The Sponsor and its agents will also be blinded to treatment assignment, with the exception of individuals who require access to patient treatment assignments to fulfill their job roles during a clinical trial. These roles include the unblinded trial statisticians, clinical supply chain managers, sample handling staff, and IxRS service provider.

Treatment Assignment

This is a randomized, double-blind study. After initial written informed consent has been obtained, an interactive voice or web-based response system (IxRS) will be used to assign a study identification number. After completion of screening procedures and assessments have been completed, and eligibility has been established for a patient, the IxRS system will be used to randomize the patient and receive treatment assignment.

Patients will be randomly assigned to one of two treatment arms: ocrelizumab or placebo. Randomization will occur in a 1:1 ratio through use of a permuted-block randomization method to ensure a balanced assignment to each treatment arm. Randomization will be stratified according to the following criteria:

- Presence of spinal cord lesions
- Presence of CSF oligoclonal bands

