To prevent potential unblinding of the assigned arm in the double-blind treatment period as a result of adverse events or changes to laboratory results, the following, additional measures have been implemented:

Blinding of laboratory parameters: Laboratory parameters that may lead to unblinding to treatment assignment, such as fluorescence-activated cell sorting (FACS) cell counts including CD19+ cells, lymphocyte count, IgM and IgG levels, will be blinded in all

patients. In order to ensure patients' safety in the study and to allow for assessments of the re-treatment criteria, a central laboratory will provide study investigators and Medical Monitors with reflex messages triggered by critical blinded laboratory results.

Investigators notified of their patient's critical laboratory test results will be instructed to suspend further treatment with study drug until the patient becomes eligible for re-treatment. The reflex messages from a central laboratory, together with non-blinded laboratory results, should be carefully reviewed at every visit before continuing with study treatment. The reflex messages will occur during the double-blind, period. During the treatment period, patients will be assessed at clinical visits as per Schedule of Assessments.

Prior to the next infusion of study drug, patients will be evaluated for pre-specified conditions and laboratory abnormalities to allow for re-treatment.

If unblinding is necessary for a medical emergency (e.g., in the case of a serious adverse event for which patient management might be affected by knowledge of treatment assignment), the investigator will be able to break the treatment code by contacting the IxRS. The investigator is not required to contact the Medical Monitor prior to breaking the treatment code; however, the treatment code should not be broken except in emergency situations.

As per health authority reporting requirements, the Sponsor's Drug Safety representative will break the treatment code for all serious, unexpected suspected adverse reactions (see Section 5.5) that are considered by the investigator or Sponsor to be related to study drug. The patient may continue to receive treatment, and the investigator, patient, and Sponsor personnel, with the exception of the Drug Safety representative and personnel who must have access to patient treatment assignments to fulfill their roles (as defined above), will remain blinded to treatment assignment.

STUDY TREATMENT

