Treatment may be stopped at any time due to lack of clinical benefit, unacceptable toxicity, withdrawal of consent, patient or physician decision to discontinue treatment, death, or if the sponsor decides to close the trial, whichever occurs first.

Treatment of Radiologic Event

In the event of radiologic progression, in which a new contrast-enhancing or T2-weighted lesion suggestive of MS develops, the choice to continue or discontinue from the study

in order to initiate treatment with a DMT, including commercial OCREVUS®, is at the discretion of the treating physician. If a commercial disease modifying therapy is initiated, the participant will be discontinued from all study-related treatments.

Regardless of whether the participant is started on commercial disease modifying therapy, individuals with a radiologic event should complete study assessments until they have completed week 208 or until they have had a confirmed clinical relapse, whichever occurs first.

As described above in Section 4.4.1 treatment may be stopped at any time due to lack of clinical benefit, unacceptable toxicity, withdrawal of consent, patient or physician decision to discontinue treatment, death, or if the sponsor decides to close the trial, whichever occurs first.

Prohibited Therapy

The following therapies for MS are not permitted during the treatment portion of the study (through week 72): Other B-cell targeted therapies (e.g., rituximab, atacicept, belimumab, or ofatumumab, etc.), natalizumab, fingolimod, siponimod, alemtuzumab, daclizumab, cladribine, teriflunomide, dimethyl fumarate, diroximel fumarate, ozanimod, interferons, glatiramer acetate, cyclophosphamide, mitoxantrone, azathioprine, mycophenolate mofetil, cyclosporine, methotrexate, total body irradiation, bone marrow transplantation, IV Ig, plasmapheresis, other approved or investigational therapies for MS.

After patients have completed (or discontinued) treatment with study drug, they may receive alternative treatment for MS as judged clinically appropriate by the investigator. However, as sufficient data are not available regarding risks associated with switching to other products, the following recommendations are given:

Caution is advised if patients remain B-cell depleted.

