For this study, a neurologic event consistent with CNS demyelination is defined as the occurrence of new and/or worsening neurological symptoms suggestive of MS. Symptoms must persist for >24 hours and should not be attributable to confounding clinical factors (e.g., fever, infection, injury, adverse reactions to medications) and be immediately preceded by a stable or improving neurological state for least 30 days. The new or worsening neurological symptoms must be adjudicated by a Sponsor-appointed adjudication committee, comprised of three expert neuroimmunology clinicians, who will review documentation associated with the event and confirm whether a relapse has occurred. Confirmed relapses will contribute to the primary endpoint.

Investigators will also screen patients for signs and symptoms of worsening neurological function localized to the cerebral cortex, such as cortical symptoms/signs, behavioral and neuropsychological alteration, retrochiasmal visual defects, hemiparesis, and cerebellar symptoms/signs (e.g., gait abnormalities, limb incoordination). Patients with

suspected PML should be withheld from ocrelizumab treatment until PML is ruled out by complete clinical evaluation and appropriate diagnostic testing (see Appendix 7). A patient with confirmed PML should be withdrawn from the study. PML should be reported as a serious adverse event (with all available information) with immediate notification of the Medical Monitor.

If an investigator determines that further testing (e.g. MRI) is necessary to evaluate a neurologic event, this would be performed according to standard of medical care. Results from any clinically warranted MRIs will be recorded in the eCRF.

Clinical neurologic events (i.e., regardless of whether they meet criteria for a protocol-defined neurologic event) will be recorded in the eCRF.

Laboratory, Biomarker, and Other Biological Samples

Samples for the laboratory tests will be collected on the days indicated in the schedule of activities (see Appendix 1).

Pre-infusion laboratory test results need to be available for review before each infusion, unless otherwise specified.

Samples for the following laboratory tests will be sent to the sites' local laboratory for analysis according to the appropriate SOA unless otherwise indicated (further details will be provided in the laboratory manual).

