Hematology: hemoglobin, hematocrit, RBC, WBC (absolute and differential: neutrophils, eosinophils, basophils, monocytes, lymphocytes, other cells), and quantitative platelet count

Quantitative Immunoglobulin (local lab evaluation at screening visit only): Ig levels (including Total Ig, IgG, IgM, and IgA isotypes).

Blood chemistry: AST, ALT, total bilirubin, urea or BUN, creatinine, potassium, sodium, calcium

Urinalysis: A urine dipstick will be performed at the site (pH, specific gravity, glucose, protein, ketones, blood), and a microscopic examination if abnormal and applicable will be performed at the site

Pregnancy test: All women of childbearing potential will have a serum pregnancy test at screening. Urine pregnancy tests will be performed at specified subsequent visits. If a urine pregnancy test is positive, it must be confirmed by a serum pregnancy test.

All women of childbearing potential must have regular pregnancy tests. A urine pregnancy test (sensitivity of at least 25 mU/mL β -hCG) will be performed locally at the timepoints shown in Appendix 1. On infusion visits, the urine pregnancy test should be performed prior to the methylprednisolone infusion. A positive urine pregnancy test

should be confirmed with a serum test through the central laboratory prior to any further dosing with study drug. If a urine pregnancy test is positive, the patient will not receive the scheduled dose, and a confirmatory serum pregnancy test will be performed by the central laboratory.

Viral serology and detection: All patients must have negative HBsAg test result at screening prior to enrollment. If total HBcAb is positive at screening, hepatitis B virus (HBV) DNA measured by PCR must be negative to be eligible.

Liver function (i.e., ALT/SGPT, AST/SGOT, total bilirubin) should be reviewed throughout the study. Patients who develop evidence of liver dysfunction should be assessed for viral hepatitis and, if necessary, referred to a hepatologist or other appropriately qualified expert. Study drug should be withheld until the diagnosis of viral hepatitis has been excluded. Patients who develop hepatitis B should be withdrawn from the study treatment. Should treatment for hepatitis be prescribed, this will be recorded in the eCRF. Patients with viral hepatitis due to other agents, such as hepatitis A, may resume study treatment after recovery.

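### Lymphocyte count is to be blinded, but post-dose white-cell differentials go to the sites' local laboratories and no supplied passage says how they are masked

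*Combined protocol and SAP*

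**What the plan says.** - **Method of Treatment Assignment and Blinding (Section 4.2).** "Study site personnel and patients will be blinded to treatment assignment until after the primary analysis". Under Blinding, both the Treating and the Examining Investigator must be blinded.
- **Blinding of laboratory parameters (same section).** To prevent unblinding in the double-blind treatment period, parameters that could reveal the arm, "such as fluorescence-activated cell sorting (FACS) cell counts including CD19+ cells, lymphocyte count, IgM and IgG levels, will be blinded in all" patients. For safety, "a central laboratory will provide study investigators and Medical Monitors with reflex messages triggered by critical blinded laboratory results". Sites are told to review those messages together with the results that are not blinded.
- **Laboratory, Biomarker, and Other Biological Samples.** A first group of tests goes to the sites' "local laboratory for analysis according to the appropriate SOA unless otherwise indicated", with a pointer to the laboratory manual for details. Hematology in that group includes "WBC (absolute and differential: neutrophils, eosinophils, basophils, monocytes, lymphocytes, other cells), and quantitative platelet count". The next item carries a limit: "Quantitative Immunoglobulin (local lab evaluation at screening visit only". A second group, sent to the central laboratory, the Sponsor or a designated processing site, holds immunoglobulins and the CD19/B-cell panel. It contains no hematology.
- **Appendix 1.** The hematology row is marked as local laboratory. Its footnote j lists absolute and differential white cells, and names absolute neutrophil count separately.
- **Review by sites.** Study Assessments makes dosing conditional on acceptable local values, and the laboratory section asks for pre-infusion results to be available for review.
- **Exclusion Criteria.** One laboratory exclusion is "Absolute lymphocyte count below lower level of normal", so each site also holds a screening count for every patient.

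**The concern.** The protocol itself judges lymphocyte count to be potentially unblinding, so no outside evidence is needed to put it on the list. A site that follows Appendix 1 literally would still receive that count after dosing, could compare it with the patient's own screening value, and would be expected to look at it before infusing. The person who looks is likely to be the Treating Investigator, who makes treatment decisions partly from laboratory findings and also evaluates patients for neurologic events at each visit.

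Two routes to the primary endpoint remain open:

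- A Treating Investigator who suspects the arm may be quicker or slower to recognize and refer a possible clinical event. Adjudication can reject a referred event but cannot recover one that was never referred.
- The investigator may withdraw a patient from the study at any time, and study withdrawal censors the patient in the primary analysis.

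**Working it through.** No arithmetic beyond a visit count applies. The check sets the blinding list against the sample routing.

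**Step 1: routing of each parameter named for blinding**

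| Parameter | Post-dose routing (laboratory section and Appendix 1) | Kept from the site as written? |
|---|---|---|
| FACS counts including CD19+ | Central, Sponsor or designated processing site | Yes |
| IgM, IgG | Local at screening only; central from baseline | Yes |
| Lymphocyte count | Within the local hematology differential; not on the central list | No |

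Only the laboratory section names lymphocytes as a component of the differential. The Appendix 1 row and footnote j reach them through the word differential.

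**Step 2: visits affected**

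Entries in the Appendix 1 hematology row after the first dose are Weeks 2, 24, 48, 104, 156, 182 and 208, which makes 7 scheduled visits. Unscheduled and completion/early-termination visits are additional. Weeks 72 and 130 have no entry.

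The Blinding section speaks of the double-blind treatment period, which can be read in two ways:

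- Treatment portion only. Prohibited Therapy describes its restrictions as applying "during the treatment portion of the study (through week 72"). On this reading Weeks 2, 24 and 48 are in scope: 3 visits.
- The whole double-blind phase of Appendix 1: all 7 visits, adding 7 − 3 = 4 (Weeks 104, 156, 182 and 208).

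The three visits in scope on either reading are all infusion visits, where results are to be reviewed beforehand.

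**Step 3: is there a masking step?**

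Reflex messages are alerts about results that are already blinded. They do not explain how a local report is masked. No supplied passage suppresses part of a local report or assigns an unblinded reviewer to it.

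**Step 4: can the effect be sized?**

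No. The documents give B-cell depletion by 14 days after treatment, but no change in total lymphocyte count by arm. They give about 21 planned primary events without a split between radiologic and clinical. They give no rate of biased referral or withdrawal.

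**The case against.** Four points can be made for the plan.

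1. *The list means cytometry output only.* Lymphocyte count follows the FACS counts, and the section expects some results to stay unblinded. This is strained: IgM and IgG stand in the same list and are not cytometry outputs. The section also never says which group the routine differential belongs to.
2. *The documents already resolve it.* Local routing holds only unless otherwise indicated, and the Blinding section may be that indication, with report suppression left to the laboratory manual. This stands in part. Masking in the manual cannot be excluded, and a reader who inferred that no masking exists would go beyond the documents. But neither the Blinding section nor footnote j points to the manual for masking, and the schedule as written delivers the count.
3. *The endpoint is protected.* Efficacy MRI is read centrally. Clinical events go to a three-member committee. The Examining Investigator sees only neurological examination, FSS, EDSS and SDMT data. Starting another MS therapy follows a treatment-policy strategy. The background section reports radiologic progression in about two-thirds of patients with RIS and a first clinical event in about one-third within 5 years, so centrally read events may form much of the composite. This stands, and it is why the effect is judged small.
4. *Full redaction is not workable.* Total white cells minus neutrophils equals lymphocytes plus monocytes, eosinophils, basophils and other cells. Removing everything from which the count could be inferred would therefore withhold total white cells or neutrophils, which sites may need for safety. This stands, so the fix below does not ask for it.

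**Conclusion.** The concern holds as a conflict between stated rules: the Blinding section hides a result that the laboratory section and schedule send to blinded staff at 7 scheduled post-dose visits, 3 of them in scope on any reading. It should be corrected, but the effect on the primary endpoint is probably small and cannot be quantified from the documents. The remaining exposure is the Treating Investigator's recognition and referral of clinical events, and study withdrawal.

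A reader might infer that sites will in practice know the arm, or that the primary comparison is compromised. The documents do not support either. They do not show how far a routine count separates the arms, and most of the endpoint's assessment lies beyond the Treating Investigator's reach.

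The conclusion assumes that the laboratory manual does not already mask local reports and that the hematology row of Appendix 1 has been read correctly from the extracted table.

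**What to change.** Reconcile the Blinding section, Study Assessments, the laboratory section, the Appendix 1 hematology row and footnote j, so that lymphocyte values after the first dose are not reported to blinded site staff. Choose one route:

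- **Central routing.** Send the post-baseline differential to the central laboratory under the existing reflex-message process. The costs are slower turnaround before infusions and probably a new Week 2 shipment. The blood and serum biomarker rows show samples at Weeks 24, 48, 104, 156, 182 and 208 but not at Week 2, so 6 of the 7 visits appear to have a suitable shipment already. The central immunoglobulin row has one entry too many for its columns in the extracted text, so this count should be checked against the original table. The Study Assessments sentence that refers to local values would need to be aligned on where the result comes from.
- **Local suppression.** Have the local laboratory, not site staff, leave the differential off the site report. The cost is a reporting arrangement with each laboratory, and the count may remain partly inferable from total white cells and neutrophils.

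Under either route, keep the safety results and critical-value alerts that sites need, including absolute neutrophil count. Leave dosing and re-treatment rules unchanged, and keep screening counts local for eligibility. State whether the blinding runs through Week 72 or the whole double-blind phase. Unscheduled visits for reasons other than relapse follow standard of care, so neither route fully covers them, and the text should acknowledge this.

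If the laboratory manual already masks the count, a cross-reference in the Blinding section and footnote j is all that is needed.
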